3.3 Expected Duration of Subject Participation

Participation in this study will begin at the time of the patient's initial evaluation and will last through the time of their post-operative visit (approximately 6 weeks after surgery)

3.4.1 Duration of Therapy

There will only be one point of intervention, which will be on the day of the patient's surgery.

3.4.2 Duration of Follow Up

Patients will be followed only until the time of their first post-operative visit.

The clinical course of each event will be followed until resolution, stabilization, or until it has been determined that the study treatment or participation is not the cause.

Serious adverse events that are still ongoing at the end of the study period will necessitate follow-up to determine the final outcome. Any serious adverse event that occurs after the study period and is considered to be possibly related to the study treatment or study participation will be recorded and reported immediately.

4.0 PATIENT SELECTION

The form below has also been included as Appendix A:

Each of the criteria in the checklist that follows must be met in order for a patient to be considered eligible for this study. Use the checklist to confirm a patient's eligibility. The checklist must be completed for each patient and must be signed and dated by the treating physician.

Patient's Name _____

Medical Record # _____

**Research Nurse /
Study Coordinator Signature:** _____ **Date** _____

Treating Physician [Print] _____

Treating Physician Signature: _____ **Date** _____

4.1 Inclusion Criteria

Patients must meet all of the following inclusion criteria to be eligible for enrollment:

4.1.1 Women must have newly diagnosed histologically or cytologically confirmed Endometrial Cancer.

4.1.2 Women should have received no prior therapy for their disease

4.1.3 Women who are planning to undergo hysterectomy, bilateral salpingo-oophorectomy, and pelvic lymphadenectomy for the management of their endometrial cancer

4.1.4 Women must have the ability to understand and the willingness to sign a written informed consent document.

4.2 Exclusion Criteria

The presence of any of the following will exclude a patient from study enrollment.

4.2.1 Women who are receiving any other investigational agents.

4.2.2 Women with a history of allergic reactions attributed to compounds of similar chemical or biologic composition to isosulfan blue or indocyanine green or other agents used in this study.

4.2.3 Women with hypersensitivity to phenylmethane compounds, or a history of allergic reaction to iodides

4.2.4 Patients with uncontrolled intercurrent illness including, but not limited to ongoing or active infection, symptomatic congestive heart failure, unstable angina pectoris, cardiac arrhythmia, or psychiatric illness/social situations that would limit compliance with study requirements.

4.2.5 Women with a history of prior LEEP or Cone procedures performed on their cervix

4.2.6 Women with a history of lymphedema, lymphoma, or lymphatic hyperplasia (Castleman disease)

4.2.7 Women with a history of a prior malignancy

4.2.8 Women may also be excluded at the discretion of their surgeon if he or she feels that the patient is not an appropriate candidate.

4.3 **Inclusion of *Women and Minorities***

Members of all races and ethnic groups are eligible for this trial.

5.0 REGISTRATION

5.1 Registration

All subjects who have been consented are to be entered into the RedCap Database. There will be no further registration that is necessary for this study.

6.0 TREATMENT PLAN

6.1 Isosulfan Blue and Indocyanine Green

Isosulfan blue (Lymphazurin)1% is an aqueous solution that is available in the operating rooms at Cleveland Clinic Main campus and Fairview and Hillcrest campuses. It is supplied as a 5ml single dose vial, 1% aqueous solution in a phosphate buffer, and it is manufactured as a sterile and pyrogen-free product. No special storage or preparation is needed for this dye as it is stored at room temperature. Adverse effects only include hypersensitivity reactions, which occur in approximately 2% of patients. Blue discoloration of the skin may occur. No drug interactions are known [38].

Indocyanine Green is a water-soluble, tricarbocyanine dye that is comes prepared in a sterile solution containing 25mg of indocyanine green and 5% sodium iodide. No special storage is necessary for this dye. It is dissolved using sterile water and titrated to the appropriate concentration desired. For the purposes of this study, a 500µg dose will be prepared. A 25mg vial of ICG will first be reconstituted in 10cc of saline. Once dissolved, 1cc of this ICG solution will be added to 1.5cc of additional saline. This new solution will therefore contain 2.5mg of ICG in 2.5cc of saline (or 500 µg/0.5 cc). Adverse effects of ICG include anaphylactic or urticarial reactions in patients with a history of iodine allergy and these patients are therefore excluded from this study. The ICG is available in the operating rooms at both the Cleveland Clinic Main campus and Hillcrest and Fairview campuses.

6.2 Intervention

Treatment must be administered only on an inpatient basis.

Patients who consent to participate in this study will be scheduled for their procedure in the normal fashion. Procedures will not be delayed for the purpose of the study. All procedures will be performed via the surgical modality determined by the surgeon.

On the day of surgery, after the patient has been placed under general anesthesia in the operating room, she will be placed in the dorsal lithotomy position, and she will undergo a routine examination under anesthesia. The patient will be prepped and draped in the usual sterile fashion.

Depending upon the surgical modality utilized, access the intra-abdominal cavity will be obtained (either via laparotomy or minimally invasive techniques). Subsequently, attention will be turned to the cervix, where a spinal needle will be used to inject 2ml of isosulfan blue directly into the cervix (1 ml at the 3 o'clock position and 1 ml at the 9 o'clock position) and/or ICG with 0.5 ml of ICG will be injected at both the 3 o'clock and 9 o'clock positions on the cervix. Following injection, the SLN will be identified and removed in a manner consistent with the algorithm proposed by Barlin et al (see Figure 1.), with sentinel lymph nodes removed from each hemi-pelvis [29]. After all mapped nodes are removed, they will be sent for pathologic examination via frozen section. Results of this analysis will be delivered to the surgeon via telephone call into the operating room. Subsequently, hysterectomy, bilateral salpingo-oophorectomy and a complete pelvic lymphadenectomy will be performed. All specimens removed will be sent to pathology. Para-aortic lymphadenectomy will be performed if the frozen section of the sentinel lymph node comes

back positive for metastasis. Otherwise, para-aortic lymphadenectomy will be performed at the discretion of the surgeon.

If, at any time, the surgeon determines that the above protocol is inappropriate, the procedure will be varied in the best interest of the patient.

The data that will be collected falls into three categories: demographic variables, procedural variables, SLN variables. The demographic variables will be collected at the time of the patient’s initial clinic visit. These variables will include: age, race, number of prior abdominal surgeries, and medical comorbidities.

The procedural and SLN variables will be collected at the time of the procedure. The procedural variables that will be collected will include: surgical modality, total operating room time, console time (robotic)/SILS operating time, time from cervical injection to SLN inspection/detection, estimated blood loss, intra-operative complications, conversion to laparotomy (for MIS) (Figure 2.)

Figure 2. Data Collection Sheet: Procedural Variables

Patient ID	Surgical modality	Total OR time	Console/ SILS operating time	Injection – SLN detection	EBL	Complications	Conversion

The console time/ operating time (for MIS procedures) will be documented from the time that the sentinel lymph node dissection begins and include the SLN biopsy, the hysterectomy, bilateral salpingo-oophorectomy, and complete lymph node dissection. All procedural variables collected will be documented at the time of surgery by either the Gynecologic Oncology fellow or the attending surgeon. Pathologic variables will include: the number of SLN detected on each hemipelvis (both by isosulfan blue and by ICG), location of mapped SLNs, number of positive lymph nodes (both SLN and in full lymphadenectomy), total number of pelvic lymph nodes dissected, total number of para-aortic lymph nodes dissected, histologic subtype, depth of myometrial invasion, grade, tumor size, lymphovascular space invasion, final stage of disease.

Reported adverse events and potential risks of Isosulfan Blue and Indocyanine Green are described in Section 7.0.

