1.4.2 Detection Method

Blue dye alone, radioisotope alone, or combinations of both detection methods have all been utilized in the literature (see Table 1), and while the optimal strategy remains unknown, each technique has advantages and disadvantages. The major disadvantages of isotope injection are that it must be performed on either the day before or the morning of surgery. Furthermore, this must be done in the nuclear medicine department, and it therefore requires extensive logistical coordination and preparation in order to optimize results [20]. This technique can therefore be technically challenging as well as costly. The injection of dye is much simpler, as it is injected immediately prior to surgery, and additional dye can be injected if needed [19]. It is additionally less costly. While allergic reactions to dye are rare (<1%) and often mild, severe allergic reactions have been reported [19].

The evidence for the optimal technique is inconsistent, with some evidence suggesting that the detection rates are equivalent and some suggesting that the combination of isotope and blue dye injection is superior [7]. However, due to the logistical challenges and cost associated with isotope injection, the cost-benefit of adding this technique is unclear. Furthermore, evidence from gynecologic oncology literature suggests a similar learning curve for SLN biopsy, with approximately 30 cases as the plateau point [10]. Some evidence suggests that experience of the surgeon rather than detection method is the more critical factor in the detection rate [18].

[figure not shown]

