12.0 STATISTICAL CONSIDERATIONS

Numerical values will be summarized by mean and standard deviation when the data have an approximately normal distribution; otherwise they will be summarized by median and interquartile range. Normality will be evaluated through visual inspection of histograms, boxplots, and normal QQ plots. Analyses specific to each aim are listed below. Secondary multivariable analysis may include logistic regression using metastasis as the dependent variable with type of dy utilized, surgical modality, surgeon, tumor stage, grade and presence of lymphovascular space invasion as independent variables. Significance will be determined by a p-value less than or equal to 0.05 unless otherwise stated.

Specific Aim 1:

Sensitivity, specificity, and negative predictive value of SLN biopsy for detecting metastasis will be estimated and appropriate 95% confidence intervals for each value will be provided.

Specific Aim 2:

Sensitivity, specificity, and negative predictive value of SLN biopsy for detecting metastasis will be compared between surgical modalities using pairwise comparisons for each surgical modality. Comparisons will be performed using two sample tests of proportions based on a normal approximation. Since three such pairwise comparisons are required, significance will be determined by a Bonferonni adjusted significance level of $0.05 / 3 = 0.17$.

Specific Aim 3:

Sensitivity, specificity, and negative predictive value of SLN biopsy for detecting metastasis will be compared between injectants utilized using a two sample test of proportions based on a normal approximation.

Specific Aim 4:

Total operating room time will be estimated as a mean with 95% confidence interval if the data have an approximately normal distribution. Otherwise, the median and a bootstrapped 95% confidence interval for the median will be reported. Similar summaries will be provided for the console time (robotic)/ operating time.

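### In women given both dyes, the plan neither separates the two readings nor links node positivity to a dye, so the per-dye sensitivity and NPV compared in Aim 3 are not assured for them

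*Combined protocol and SAP*

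**What the plan says.** **Who gets which dye.** Section 6.2 describes a cervical injection of isosulfan blue "and/or ICG with 0.5 ml of ICG will be injected at both the" 3 and 9 o'clock positions. A woman may therefore have blue, ICG or both. No allocation rule and no expected share of dual-dye women are given.

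**How the dyes are read.** The next step is "Following injection, the SLN will be identified and removed in a manner consistent with the algorithm proposed by" a cited group. No imaging mode is to be read first, and nothing requires one dye's findings to be recorded before the other is viewed. Then: "After all mapped nodes are removed, they will be sent for pathologic examination via frozen section". Labelling by node or by dye is not mentioned.

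**What is recorded.** The pathologic variables in 6.2 include "the number of SLN detected on each hemipelvis (both by isosulfan blue and by ICG), location of mapped SLNs, number of positive lymph nodes", the last item reading more fully "number of positive lymph nodes (both SLN and in full lymphadenectomy". Detection is thus counted by dye and side, while positivity is counted only as SLN or full lymphadenectomy.

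**What is analysed.** Comparing injectants is a secondary objective (2.2). Under Aim 3 (12.0), sensitivity, specificity and NPV "will be compared between injectants utilized using a two sample test of proportions based on a normal approximation". Section 10.1.1 defines sensitivity per patient, among those with an SLN detected.

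**The concern.** Aim 3 needs to know, for each woman and each dye, whether that dye's SLNs included a positive node. A woman given one dye supplies this directly. A woman given both supplies it only if each positive SLN can be traced to the dye or dyes that marked it, and the listed variables do not make that link.

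Two further gaps concern the same women. Blue is seen by eye and ICG through a special camera (1.4.2, 8.2), so a node already found in one mode can prompt the surgeon to call it in the other. The two readings are then not independent. Also, if a dual-dye woman is counted under both injectants, her two results are paired, and a test for two independent samples does not fit.

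Node-positive women are few, so a handful of unassignable cases can move a per-dye estimate appreciably. The women whose dyes disagree are also the ones who carry the information in a within-woman comparison.

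**Working it through.** **1. The plan's own figure.** Section 3.2 gives 200 from a single-proportion calculation with p = 0.15, margin E = 0.05, 95% confidence and population N = 20,000. With x = 1.96² × 0.15 × 0.85 = 0.4898, n = N·x / ((N − 1)·E² + x) = 9,796 / 50.487 = 194.03, rounded up to 195. The stated 200 is consistent with this. It says nothing about the injectant comparison, for which no figure is given.

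**2. Can the dye be traced?** Take a woman with one blue-only SLN on the right, one ICG-only SLN on the left, one positive SLN and no other positive node.

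| | Right node positive | Left node positive |
|---|---|---|
| Blue count, right / left | 1 / 0 | 1 / 0 |
| ICG count, right / left | 0 / 1 | 0 / 1 |
| SLN locations | right, left | right, left |
| Positive SLNs | 1 | 1 |
| Blue result | finds the metastasis | misses it |
| ICG result | misses it | finds the metastasis |

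The listed record is identical in both columns, but the per-dye results are opposite.

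**3. Where the gap stops.** Per-dye results can be worked out:
- for every woman given one dye;
- for a dual-dye woman in whom only one dye mapped;
- when no SLN is positive;
- when all SLNs are positive.

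What remains is dual-dye women whose dyes mapped different SLNs and in whom only some SLNs are positive, apart from cases where the counts alone force the answer.

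**4. How many node-positive women there are.** Section 3.2 cites positivity of 9% and 13% and uses 15%. Detection is 78% in the meta-analysis and 92% in one Table 2 study (1.3). Mapped node-positive women: 200 × 0.09 × 0.78 = 14.0 up to 200 × 0.15 × 0.92 = 27.6.

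**5. Illustration of the effect.** Assume that all 200 women receive both dyes, both dyes map in the same women, positivity is 13% and detection 92%. Mapped node-positive women: 200 × 0.13 × 0.92 = 23.9, say 24. Mapped node-negative women: 174 × 0.92 = 160. At 89% overall sensitivity (the same Table 2 study, which used isotope), 0.89 × 24 = 21 are SLN-positive and 3 are false negatives. Suppose a share u of the 21 is unassignable, and the rest are credited to the dye in question. Its sensitivity then runs from (21 − 21u)/24 to 21/24. Its NPV, taken as true negatives over all SLN-negative women, runs from 160/(160 + 3 + 21u) to 160/163.

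| u (assumed) | Unassignable | Sensitivity | NPV |
|---|---|---|---|
| 0% | 0 | 88% | 98.2% |
| 10% | 2 | 79–88% | 97.0–98.2% |
| 20% | 4 | 71–88% | 95.8–98.2% |
| 40% | 8 | 54–88% | 93.6–98.2% |

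**6. Direction of any reading bias.** Let the dyes detect independently with probabilities p₁ (read first) and p₂ (read second), and let a share s of the second dye's misses that were found by the first be called anyway. The second dye's apparent detection is p₂ + (1 − p₂)·p₁·s, so only the second-read dye gains. The gap narrows if the weaker dye is read second and widens if the stronger is. With assumed rates of 90% for ICG and 75% for blue, s = 0.3 to 0.6 and blue read first, ICG appears as 0.90 + 0.10 × 0.75 × s = 92.3% to 94.5%. The 15-point gap widens to about 17 to 19.5 points. The plan fixes no order, so the sign is unknown.

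**7. What a paired test could show.** An exact McNemar test with k discordant women, all in one direction, gives p = 2 × 0.5^k: 0.0625 for k = 5 and 0.031 for k = 6. At least 6 are needed.

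**The case against.** The strongest reply is that the plan never states a within-woman comparison. Section 12.0 lists dye type as a patient-level covariate, so blue-only, ICG-only and both could be three groups of women. That fits the per-patient definitions in 10.1.1 and needs no node-level attribution. This stands as a workable analysis, but the plan does not specify it. It would also leave unused the per-dye counts that 6.2 collects in dual-dye women.

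It can also be said that the variable list may not be exhaustive, that all specimens go to pathology, and that SLN location is recorded. Some links might therefore be recovered from source documents. That is possible, but the plan does not call for it, and the order of reading cannot be recovered later.

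Three stronger readings are tempting, and the documents do not support them:
- A reader might infer that per-dye sensitivity cannot be computed at all. Step 3 shows that the gap is confined to one subset of dual-dye women. Per-dye detection is recorded.
- A reader might infer that unmasked reading pulls the two dyes together. Step 6 shows that the direction depends on which is read first. That arithmetic also concerns detection, which Aim 3 does not list.
- A reader might infer that a second dye will be added when the first fails. The remark in 1.4.2 that "additional dye can be injected if needed" is background on why dye is simpler than isotope. It is not a study instruction and does not speak of a second agent. For a hemi-pelvis that does not map, the algorithm in 1.4.3 calls for lymphadenectomy on that side.

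**Conclusion.** The point holds in a limited form. For dual-dye women the plan requires no independent reading of each dye, does not record SLN positivity by dye or by node, and does not say how these women enter the two-sample test. Where the dyes mapped different SLNs with mixed pathology, per-dye true positives and false negatives generally cannot be assigned from the listed variables.

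The size is unknown, because neither the dual-dye share nor the frequency of such discordance is stated. The ranges in step 5 rest on every woman having both dyes and on an assumed 10% to 40% unassignable. With few dual-dye women the effect would be small.

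This affects a secondary objective, and better records will not make Aim 3 well powered. With 7 to 14 mapped node-positive women per dye (single dye, 1:1 split assumed), power for 84% versus 93% sensitivity is about 7% to 11% at two-sided 0.05, and 80% power would need 197 per dye. The change is still worth making, because the data must be captured at surgery.

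**What to change.** **Section 6.2, records.** Replace the aggregate SLN counts with one line per SLN: side, location, blue yes/no, ICG yes/no, mode read first, metastasis yes/no. Record the dye or dyes given to each woman, so that a zero count for a dye can be told apart from a dye not given.

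**Section 6.2, reading.** For women given both dyes, write down the blue-visible nodes before near-infrared viewing. This protects the blue reading only. ICG is still read with knowledge of blue, and the report should acknowledge that remaining dependence.

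**Section 10.1.1.** State the per-dye definitions for dual-dye women, including how a dye is scored when its own SLNs are negative and the only positive node was mapped by the other dye.

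**Section 12.0, Aim 3.** Compare blue-only with ICG-only women by the two-sample test. Analyse dual-dye women separately, and do not count them in both arms of that test. For sensitivity, use an exact McNemar comparison among node-positive women mapped by both dyes. NPV has a different denominator for each dye, so McNemar does not apply to it directly; report the paired difference with a bootstrap interval that resamples women.

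**Cost.** A few more RedCap fields, a short added step in theatre, node-by-node labelling for pathology, and a paragraph in 12.0. Splitting the women into groups makes each comparison smaller, and dye choice remains non-randomised.

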6.3 Duration of Therapy

There will only be one point of intervention, which will be on the day of the patient’s surgery.

6.4 Duration of Follow Up

Patients will be followed only until the time of their first post-operative visit.

The clinical course of each event will be followed until resolution, stabilization, or until it has been determined that the study treatment or participation is not the cause.

Serious adverse events that are still ongoing at the end of the study period will necessitate follow-up to determine the final outcome. Any serious adverse event that occurs after the study period and is considered to be possibly related to the study treatment or study participation will be recorded and reported immediately.

7.0 ADVERSE EVENTS: LIST AND REPORTING REQUIREMENTS

The following is a list of AEs (Section 7.1) and the reporting requirements associated with observed AEs (Sections 7.3 and 7.4).

The clinical course of each event will be followed until resolution, stabilization, or until it has been determined that the study treatment or participation is not the cause.

Serious adverse events that are still ongoing at the end of the study period will necessitate follow-up to determine the final outcome. Any serious adverse event that occurs after the study period and is considered to be possibly related to the study treatment or study participation will be recorded and reported immediately.

